European Society of Cardiology conclusively demonstrated that surgical occlusion of the LAA markedly decreased the risk of stroke in comparison to controls: at 3.7 years 6% in patients with no LAA versus 18% in the control population(42).

[figure not shown]

Figure 2. Pulmonary vein isolation procedure

Hypothesis

We hypothesize that performing a prophylactic limited left sided surgical maze, i.e., pulmonary vein isolation and excision of the left atrial appendage, in a group of at risk cardiac surgical patients at the time of the index procedure, will reduce the incidence of POAF. The null hypothesis is that the prophylactic surgical ablation will have no effect on the incidence of POAF.

Setting of the Research

This study will be conducted at a single center, Spectrum Health. The PI and all Spectrum Health cardiothoracic surgeons participating in the study are highly qualified and certified by the American Board of Thoracic Surgery. They are all proficient in performing the maze procedure as it is commonly utilized in everyday practice to manage and treat AF.

Subjects will be seen in the cardiothoracic surgeon's office and/or the hospital inpatient setting. The surgery will be performed at the Meijer Heart Center, Spectrum Health Hospitals.

Resources Available to Conduct this Research

Spectrum Health cardiothoracic surgeons perform approximately 1200 heart surgeries per year. Approximately 300 of these surgeries which include isolated coronary artery bypass grafting (CABG), isolated aortic valve replacement (AVR), or combined AVR/CABG are performed in patients ≥ 70 years of age. Therefore, we do not anticipate difficulty recruiting the necessary number of subjects during the enrollment period.

The PI will have dedicated research time in his schedule. Experienced research staff from the CV Structural Heart Team will assist with the study as delegated by the PI.

Study Design

This is a single-center, prospective, randomized, unblinded, interventional feasibility study to determine whether or not a prophylactic limited left sided surgical maze procedure is effective in reducing or preventing POAF. A high risk population with no history of atrial fibrillation or flutter, with a baseline risk of POAF of 40% or greater will be chosen. This includes CABG/AVR, isolated AVR, and isolated CABG patients 70 years and older. Up to 60 subjects who are scheduled to undergo elective open heart surgery will be randomized 1:1 into one of two study arms:

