- 1. Control arm: Elective open heart surgery without a limited left sided maze procedure.
- 2. Treatment arm: Elective open heart surgery with a limited left-sided maze procedure.

Sample Size Determination

No sample size calculation was performed as this is a feasibility trial and the number is fixed at 60 patients where 30 will be randomly assigned to the control arm and 30 randomly assigned to the treatment arm.

Statistical Methods

Summary statistics will be calculated. Quantitative variables will be expressed as mean ± standard deviation or median [interquartile range]. Qualitative variables will be expressed as frequency (percent). To determine if there is an association in POAF and the two arms of the study, a Chi-Square Test or Fishers Exact test will be used depending on assumptions being met. To look at our secondary outcomes such as hospital length of stay and incidence of postoperative reoperations for bleeding, a two sample t-test or Wilcoxon Rank Sum will be used to determine if there is a difference between the two groups and those that had POAF vs. those that didn't. Significance will be assessed at the 0.10 level. A level of 0.10 will provide more power to the study while only allowing a slight increase in error.

Recruitment methods

All subjects who receive an inpatient or outpatient heart surgery consult and meet the criteria may be approached about study participation. Consults will occur in the Cardiothoracic Surgeon's office of the Meijer Heart Center or Spectrum Health inpatient units. The subject's electronic medical records (EMR), Cerner and Epic, will be reviewed. There are no plans for advertisement or patient payment related to study participation.

It is expected enrollment will take approximately 6 months.

Inclusion and Exclusion criteria

Inclusion Criteria

- 1. Male or female
- 2. Age \geq 70 years
- 3. Elective cardiac surgery: isolated AVR, isolated CABG, or AVR/CABG,

Exclusion Criteria

- 1. A history of AF or atrial flutter
- 2. Less common cardiac operations such as aortic root replacements, aortic dissections, myxoma excisions, or pericardectomies. Beating heart or off-pump procedures, redo open heart procedures.
- 3. Subjects with existing pacemaker and/or AICD
- 4. Vulnerable populations; adults unable to sign consent, prisoners
- 5. Need for emergent or salvage surgery for any reason
- 6. Currently participating in an investigational drug or another device study (excluding registries)

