- 7. Subjects currently on antiarrhythmic drugs Class I and III including amiodarone.

Study endpoints

The incidence or absence of documented AF, defined by Society of Thoracic Surgeons (STS) registry data as the occurrence of POAF or atrial flutter that requires treatment, is the primary endpoint (21). In addition, length of stay (LOS) and additional antiarrhythmic or anticoagulant medications will be examined as a secondary endpoint.

Safety endpoints

The safety endpoint is the occurrence of one of the following events between time of procedure and the 30 day post procedure assessment:

- All-cause death
- TIA/stroke
- Bleeding (chest tube drainage) that is procedure related and requires take back to the operating room or blood transfusions
- Incidence of AF
- Need for permanent pacemaker
- Evidence of pulmonary vein stenosis defined as > 50 % occlusion of the vessel.

Procedures Involved in the Research

Baseline preoperative cardiac surgery workup will be done on all patients according to standard of care. This workup will consist of:

- History and physical exam
- Chest X-Ray

- Electrocardiogram
- Echocardiogram
- Cardiac catheterization
- Blood and urine tests such as complete blood count, complete metabolic count, cardiac enzymes, type and screen, and urinalysis. Any other indicated tests based on patient history and index procedure i.e.; pulmonary function tests, carotid ultrasound, leg vein mapping, noncontrast chest CT.

Prior to enrollment, the protocol and informed consent must be approved by the Spectrum Health Institutional Review Board (IRB). IRB approved Health Insurance Portability and Accountability Act (HIPPA) will also be used. A regulatory binder and subject binders will be created according to local requirements and stored in the CV Research Department.

Before the subject signs the informed consent form (ICF), the investigator or designated study personnel will explain the research, study procedure, anticipated benefits, and potential risks of study participation. Adequate time will be allowed to read the ICF and ask questions. The original signed ICF will be kept with the subject's research records and a copy will be given to the subject.

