- Medications, pre- and post-op including name of medication, indication, dose.
- Procedure and date- including number of grafts and type of valve implanted
- CPB time, X-clamp time
- EKG rhythm(s), pre- and post-op (atrial flutter, SVT, VT, etc.)
- Post procedural stroke/TIA
- Post procedural MI
- Post procedural pacemaker implant
- Any bleeding complication
- Any incidents of POAF (date occurred, treatment used,)
- Length of stay

Data will also be collected at 6 weeks, 6 months and 12 months post-procedure. This will include:

- All adverse events
- Any rehospitalizations
- Medications, current and new
- Any episodes of AF or other cardiac arrhythmias
- EKG
- Need for pacemaker

• Echocardiogram: EF, valve gradients, left and right atrial function, pulmonary vein stenosis or presence of suspected thrombus.

In the event that we are unable to find subject information in the EMR at appointed study intervals, we may telephone subjects to inquire how they are and whether or not they have had any adverse events.

Assessments/procedures	Baseline	Hospitalization	Predischarge	Follow up	Follow up	Follow up
	Screening			6 weeks	6 months	12 months
				post	post	post
				procedure	procedure	procedure
				+/-7 days	+/- 7 days	+/- 7 days
Consent	Х					
History/Inclusion and	Х					
Exclusion						
Medication Review	Х	X		X	X	X
Randomization	Х					
AF occurrence and		X		X	X	X
treatment						
Transthoracic echo			X			
			Treatment			
			arm only			
Rehospitalizations				X	X	X
Adverse Events		X		X	X	Х

Adverse events

An adverse event (AE) is any untoward medical occurrence (signs, symptoms, abnormal laboratory findings) in a subject. It does not necessarily have to be caused by the device or procedure to be considered an adverse event.

A serious adverse event is one that led to death, serious deterioration in the health of the subject, resulted in a new hospitalization or prolonging the index hospitalization, a permanent impairment of a body structure or function, or required medical and/or surgical intervention to prevent further lifethreatening illness or injury

A device related adverse event is an event that in the investigators judgement may be related to the investigational device.

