Data will be reviewed by a non-study cardiothoracic surgeon; [name]. The review will include subject eligibility, documentation of the consent process, adverse events, and subject withdrawals. Review will occur after every 5 patients have a completed surgical procedure and are discharged from the hospital. Adverse Events (AE) will be evaluated for seriousness, unanticipated, procedural and/or device-relatedness. If any Serious Adverse Events (SAE) occur beyond what is expected in this patient population and are thought to be related to the limited left sided surgical maze procedure, the FDA and Spectrum Health IRB will be notified per reporting practices and the study may be terminated.

Monitoring of patient data will continue throughout the study at the scheduled assessment times.

Withdrawal of subjects

We do not foresee any circumstances in which subjects would want to withdraw from the study. However, subjects may withdraw from this study at any point, it will not be held against them nor involve penalty or loss of benefits to which subjects are otherwise entitled.

Risks/Benefits to Subjects

Neither LAA amputation or pulmonary vein isolation ablation, the 2 components of the limited left sided surgical maze procedure, have been shown to pose additional risk to the subject over the primary open heart procedure (7,8,16,28).

Potential adverse events with this combined procedure are similar to the risks of cardiac surgery and are listed below as described in the AtriCure® Synergy Ablation System Instructions for Use:

- Death
- Excessive bleeding that may require re-intervention
- Cardiac tamponade
- Pulmonary vein stenosis
- Restrictive or constrictive pericarditis
- Infection that may result in sepsis or endocarditis
- Myocardial infarction (MI)
- Stroke or transient ischemic attack (TIA)
- Thromboembolism
- Diaphragmatic (phrenic nerve) paralysis
- Esophageal-left atrial fistula or esophageal rupture
- Atrial perforation or rupture
- Ventricular perforation or rupture
- Atelectasis
- Pneumonia
- Congestive heart failure
- Cardiac valve injury
- Persistent pneumothorax
- Excessive pain and discomfort
- Deep sternal wound infection (mediastinitis)
- Perioperative atrial or ventricular rhythm/conduction disturbance
- Pericardial effusion
- Injury to the great vessels
- Injury to unintended surrounding tissues, including tears and punctures
- Extension of cardiopulmonary bypass time or aortic cross clamp time

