There have been reports that amputation of the LAA may increase the risk of POAF but these are not consistent and a recent meta-analysis demonstrated no increased risk of POAF (43). Further a surgical Cox maze is always defined by management of the LAA either with amputation or creation of an epicardial surgical lesion at its base and occlusion of the LAA. Long term results of the maze procedure show no ill effects to the patient and left atrial transport function is maintained (30).

Globally the AtriCure device has been safely used in over 200,000 cases and is the predominant device used to perform surgical ablation of AF in the world. Thus the safety of the AtriCure device has been outstanding with almost no risk to the patient and the ablation lesions have no late or long-term adverse effects on the myocardium.

In a study published in Circulation of over 10,000 patients who underwent amputation of the LAA there was no increased risk of bleeding (16). Multiple large studies have demonstrated that a left sided or limited left sided surgical maze procedure adds no operative risk and only improves patient outcomes, especially in regard to long term stroke risk and survival (7,8,17,28,29,44). A recent 2018 publication from the STS Adult Cardiac Database strongly corroborates LAA removal as it markedly decreased the long term risk of stroke (42).

The strongest evidence, that there is no additional risk to the patient, is put forth in the 2017 Guidelines for The Surgical Treatment of Atrial Fibrillation set by The Society of Thoracic Surgeons: "Surgical ablation for AF can be performed without additional operative risk, and is recommended at the time of concomitant isolated AVR, isolated CABG and AVR+CABG operations to restore sinus rhythm." The Society of Thoracic Surgeons labels this as a Class I recommendation; meaning that the procedure should be performed as a standard of practice because it is useful, effective, and the benefits far outweigh the risks.

A recent Russian study examining the effects of prophylactic pulmonary vein isolation with radiofrequency ablation in patients undergoing isolated CABG has shown very promising results. The incidence of POAF was reduced by 21% versus controls and at one year the effect was sustained as 98% of the prophylactic group was free from AF versus 84% of the controls. The conclusion was "simultaneous preventive pulmonary vein isolation during CABG is safe and effective" (40).

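### The 30-day safety endpoint counts AF, which the maze is meant to reduce, so the summary safety rate favours the maze arm and can hide a moderate rise in real harms

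*Combined protocol and SAP*

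**What the plan says.** The Objective gives safety and effectiveness equal standing. The Safety endpoints section states: "The safety endpoint is the occurrence of one of the following events between time of procedure and the 30 day post procedure assessment". Six events follow: death from any cause, stroke or TIA, procedure-related bleeding needing reoperation or transfusion, "Incidence of AF", a permanent pacemaker, and pulmonary vein stenosis above 50%.

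Under Study endpoints, "the occurrence of POAF or atrial flutter that requires treatment, is the primary endpoint". The Hypothesis section says the maze "will reduce the incidence of POAF". The two AF items overlap heavily but are not identical: the safety item has a 30-day window and no requirement for treatment.

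Statistical Methods provides frequency and percent for qualitative variables. It names a between-group comparison for only one non-AF safety event, the "incidence of postoperative reoperations for bleeding". No version of the safety endpoint without AF is planned. The Data management list records the components separately, for example "Post procedural stroke/TIA". Under the data-safety provisions a non-study surgeon looks at adverse events as the trial runs: "Review will occur after every 5 patients have a completed surgical procedure".

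**The concern.** A safety composite should move when the intervention does harm. This one also moves when the intervention works, and in the opposite direction. Patients are chosen for a POAF risk of 40% or more (Study Design), so AF is likely to be among the most frequent components. If the maze does what the trial hopes, the summary rate will fall in the maze arm without any difference in safety. It could look neutral or favourable while stroke, bleeding or pacemaker implantation rises. A reader of a feasibility report may take that rate as the answer to the safety half of the objective.

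**Working it through.** The plan gives no safety rate or power figure, so there is nothing of its own to reproduce.

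**Inputs from the documents**
- 30 patients per arm (Sample Size Determination).
- Control AF 40% (Study Design), varied to 30% and 60% (Background).
- A 21% reduction in POAF in a cited study of prophylactic pulmonary vein isolation (Risks/Benefits). The text does not say whether this is absolute (40% to 19%) or relative (40% to 40 × 0.79 = 31.6%).

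**Assumptions**
- AF falls from 40% to 20%, close to the absolute reading; 31.6% is used for the relative reading.
- The rate of any non-AF event, *h*, is not in the documents. The base value is 10%, varied below.
- Components are independent within a patient.
- Two-sided Fisher at 0.10 is a yardstick only; the plan assigns no test to this endpoint.

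**Composite rate per arm** = 1 − (1 − AF)(1 − *h*). The control arm at AF 40%, *h* 10% gives 1 − 0.60 × 0.90 = 46.0%.

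| Case | AF, control → maze | Other events, control → maze | Composite, control vs maze |
|---|---|---|---|
| 1. No harm | 40% → 20% | 10% → 10% | 46.0% vs 28.0% |
| 2. Harm doubled | 40% → 20% | 10% → 20% | 46.0% vs 36.0% |
| 3. Harm doubled, smaller AF effect | 40% → 31.6% | 10% → 20% | 46.0% vs 45.3% |
| 4. Harm tripled, smaller AF effect | 40% → 31.6% | 10% → 30% | 46.0% vs 52.1% |
| 5. Common bleeding | 40% → 20% | 40% → 60% | 64.0% vs 68.0% |

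**Sampling behaviour**, by exact enumeration of two binomials with n = 30 each:
- Case 1: the maze arm shows the lower rate with probability 0.91, and significantly lower with probability 0.31, with no true safety difference.
- Case 2: the maze arm shows the lower rate with probability 0.75. The chance of a significant harm signal is 0.3% with AF included and 16.2% with AF removed.
- Case 4: the direction of harm shows, but the chance of a signal is 7.1% with AF and 48.9% without.
- Case 5: a 20-point rise shrinks to 4 points; the chance of a signal is 5.5% with AF and 35.0% without.

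**Break-even**, the maze-arm rate of other events at which the composites are equal, is 1 − (1 − AF_control)(1 − *h*_control)/(1 − AF_maze). From 10% in the control arm:
- AF falling to 20%: 1 − 0.54/0.80 = 32.5%.
- AF falling to 31.6%: 1 − 0.54/0.684 = 21.1%.

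**Other control AF rates**, with other events 10% → 20%:
- AF halved from 30%: 37.0% vs 32.0%. Halved from 60%: 64.0% vs 44.0%.
- A 21% relative fall from 30%: 37.0% vs 39.0%, so the harm shows. From 60%: 64.0% vs 57.9%.

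**Dependence**, case 2. Full overlap takes the larger of the two rates: 40% vs 20%. No overlap adds them: 50% vs 40%. The maze arm looks safer at both extremes. In case 3, no overlap gives 50% vs 51.6%, so the doubling is then almost, but not fully, offset.

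**The case against.** The strongest reply is that no summary rate may ever be used this way. The heading is plural, the plan assigns the composite no test, and if the six items are reported one by one there is no masking. Components are collected separately, adverse events are reviewed individually, and any thromboembolic event triggers a report to the regulator that gives enrolment and treatment numbers by arm. Statistical Methods introduces its secondary outcomes as examples, so other by-arm comparisons are not ruled out. These points limit the harm to the summary rate. They do not remove it: the defining sentence describes one endpoint met by any one event, and monitoring is not a planned by-arm summary.

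Counting arrhythmia as a safety outcome is also defensible. Rhythm disturbance and flutter are among the listed risks, and "There have been reports that amputation of the LAA may increase the risk of POAF but these are not consistent". If AF did not fall, the bias would vanish: with AF at 40% in both arms and other events 10% → 20%, the composite is 46% vs 52%. This supports reporting AF as a safety outcome, but in its own row, where a rise would be easier to see than inside a composite.

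The illustrations do rest on an assumed 10% rate for other events. Because transfusion counts as bleeding, the true rate could be much higher, and masking then weakens. With AF 40% → 31.6% and other events 20% → 40%, the composite is 52% vs 59%, so harm shows, though diluted. That stands as a limit on size.

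**Conclusion.** The concern holds and should be fixed. Whenever the maze lowers AF and other harms are equal, the safety rate as defined favours the maze arm; this direction does not depend on the assumed rates. How much harm it can offset does. From an assumed 10% of other events and 40% control AF, the offset reaches about a doubling (break-even 21.1%) if the cited 21% is relative, and about a tripling (32.5%) if AF halves. It is smaller when control AF is lower or bleeding is common. The distortion is confined to the summary rate, since the individual events remain recoverable.

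**What to change.** Remove AF from the composite. Define the composite as any of death, stroke or TIA, procedure-related bleeding as already worded, permanent pacemaker, or pulmonary vein stenosis, within the stated 30-day window. Report the composite and each component by arm as counts and percentages with exact 95% confidence intervals, labelled descriptive. Report 30-day AF by arm, treated and untreated, in its own row beside the primary endpoint, so that any pro-arrhythmic effect stays visible. If the six items were always meant as separate endpoints, say so and reword the defining sentence so that it no longer describes a composite.

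The cost is one bullet moved and two or three sentences of analysis text. AF episodes with their treatment, and the other components, are already on the data list, so this change needs no new collection. The downside is fewer events and wide intervals: 3/30 has an exact 95% interval of 2.1% to 26.5%, and 6/30 of 7.7% to 38.6%. The trial will still have little power to show harm, but the rate will no longer be pulled in the maze's favour.

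Three neighbouring matters are not settled by this change: the scheduled pre-discharge echocardiogram is in the treatment arm only, small transfusions for anaemia are exempt from adverse event reporting, and the 30-day point is counted from the procedure in one place and from discharge in another.

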Postoperative monitoring, diagnostic and lab tests will be done according to Spectrum Health standard of care. Current standard of care for the postoperative cardiac surgery patient at this institution consists of continuous telemetry monitoring, collection of arterial blood gases, complete blood count, basic metabolic panel and blood glucose at regular intervals. An EKG is obtained on arrival to the recovery area and any time a cardiac dysrhythmia is noted.

In addition to standard of care, subjects who were randomized to the treatment arm of the study will have a pre-discharge transthoracic echocardiogram to assess the absence or presence of thrombus in the left atrium. If thrombi are noted, subjects will be anticoagulated per standard of care.

The highest risk of POAF is within the first 48 to 96 hours after surgery. All post-operative patients are on continuous 24 hour telemetry after surgery until hospital discharge. While it depends on the index procedure that was done, the usual length of stay at this institution following elective cardiac surgery is 5 to 7 days.

If subjects develop POAF, paroxysmal or sustained, they will be treated with standard medications and protocols already in place for this complication.

The current protocol to treat POAF first entails escalation of beta blocker therapy if it is tolerated. If further treatment is necessary, patients are loaded with a dose of IV amiodarone and then changed to oral amiodarone for four weeks or longer if appropriate.

Our current standard of care at Spectrum Health for POAF anticoagulation is as follows. For POAF that persists for more than 24 hours or is episodic and occurs more than once, anticoagulation is initiated. Warfarin or one of the new oral anticoagulants such as dabigatran, rivaroxaban or apixiban will be used tailored to the individual patient utilizing their CHA2DS2-VASc score and surgeon preference.

In addition, all patients who receive a mechanical valve or a bio prosthetic mitral valve are started on an anticoagulant on postoperative day 2. The dose is titrated to an INR of 2.5-3.5.

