To our knowledge isolated radiofrequency epicardial pulmonary vein lesions have not resulted in endocardial thrombus. Nor has this been reported with the AtriCure clamp. The current recommendations are to anticoagulate patients who undergo surgical ablation with endocardial lesions or full surgical Maze procedures which involve additional lesions in the left and/or right atrium (35,36). At Spectrum Health we perform 1200 open heart surgery procedures per year and it is not our standard to anticoagulate patients after isolated PVI who remain in sinus rhythm except for a daily aspirin. Of note all cardiac surgical patients are on daily Lovenox postoperatively to prevent deep venous thrombosis.

Subjects will be visited daily by research staff during the index hospitalization. The EMR will be reviewed with a focus on any episodes of POAF or any other cardiac dysrhythmias, any need for pacemaker, chest tube drainage or need for blood transfusion beyond what is normal for this patient population.

The initial follow-up for POAF occurrence will be 30 +/-7 days post hospital discharge; this is standard for post-operative surgical care. Additional follow-up, consisting of electronic medical record (EMR) review anywhere care is given, will occur at 6 weeks, 6 months and 12 months post procedure. Review of subject data will include any adverse events that may have occurred, EKG, and echocardiogram review. If data is not available in the EMR, phone calls will be made to subjects.

Data management

Research Electronic Data Capture (REDCap) will be used for randomization and data collection. REDCap is password protected and only IRB study approved personnel will have access to the data.

Standard practice is to enter this group of surgical patient's information into the Society of Thoracic Surgeons (STS) Registry. Subjects in this study will be included in the STS Registry.

Data to be collected will include:

- Subject name, date of birth and medical record number
- Gender, age
- Inclusion/Exclusion criteria
- Medical History: hypertension (HTN), diabetes mellitus (DM), hypercholesterolemia, chronic lung disease, peripheral vascular disease (PVD), coronary artery disease (CAD), CHF, chronic kidney disease (CKD), cerebrovascular disease (stroke/TIA)
- Echocardiogram (pre-op and pre-discharge (treatment arm only)): EF, LA measurement, LV measurement, mitral regurgitation, tricuspid regurgitation

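### Pulmonary vein stenosis counts as a safety event only to the 30-day assessment, but no vein examination is planned by then and the plan names it as a data item only at later record reviews

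*Combined protocol and SAP*

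**What the plan says.** The objective covers safety as well as effectiveness. *Safety endpoints* sets the window once for all components: "The safety endpoint is the occurrence of one of the following events between time of procedure and the 30 day post procedure assessment". The last of the six events listed is "Evidence of pulmonary vein stenosis defined as > 50 % occlusion of the vessel".

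The other relevant text, all in the combined protocol and SAP:

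- *Procedures Involved in the Research*: beyond standard care, treatment-arm subjects "will have a pre-discharge transthoracic echocardiogram to assess the absence or presence of thrombus in the left atrium". This is the only echocardiogram after surgery that the study itself requires.
- *Data management*, first list, gives the fields for that echo: "Echocardiogram (pre-op and pre-discharge (treatment arm only)): EF, LA measurement, LV measurement, mitral regurgitation, tricuspid regurgitation". The veins are not among them. The same list has items for stroke/TIA, pacemaker, bleeding and post-operative AF, but none for stenosis.
- *Procedures Involved in the Research*, follow-up text: "The initial follow-up for POAF occurrence will be 30 +/-7 days post hospital discharge". No imaging is attached to this visit. Later follow-up is by medical record, with phone calls where the record is silent: "Review of subject data will include any adverse events that may have occurred, EKG, and echocardiogram review".
- *Data management*, second list: "Data will also be collected at 6 weeks, 6 months and 12 months post-procedure". Here stenosis appears as a data item: "Echocardiogram: EF, valve gradients, left and right atrial function, pulmonary vein stenosis or presence of suspected thrombus". The assessment table shows no echocardiogram after the pre-discharge one.
- *Adverse events*: collection runs from surgery to 365 days. Events are classified by seriousness and by relation to device or procedure.
- *Risks/Benefits to Subjects*: stenosis is listed as a possible risk of the maze procedure. The section also says that no case above 50% has been documented and puts the risk of any complication below 1%.

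**The concern.** The endpoint and the data collection do not line up for this one component. The endpoint stops counting at 30 days, while the plan starts recording stenosis by name at 6 weeks and continues to 12 months. Under the stated rule, a stenosis first found at the 6- or 12-month review is in the database but not in the safety endpoint.

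Conversely, a 30-day count of zero would come from a period in which nobody was asked to look at the veins. Stenosis is a risk of the ablation, which only treated patients receive, and these patients have no history of AF. A bare zero could be read as support for the protocol's statement that no cases are documented, although the veins may not have been examined.

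**Working it through.** The plan gives no rate, precision or sample size calculation for stenosis, so there is no figure to reproduce. The check compares timings and then asks how much a zero could say.

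**1. Timing.** *Safety endpoints* counts 30 days from the procedure. The follow-up text puts the first visit 30 ± 7 days after discharge, with a usual stay of 5 to 7 days.

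- First visit, counted from surgery: 5 + 23 = day 28 to 7 + 37 = day 44. On target it is 5 + 30 = day 35 to 7 + 30 = day 37.
- 6-week review: 42 − 7 = day 35 to 42 + 7 = day 49.

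If the 30-day assessment is the post-discharge visit, the 6-week review can overlap it. The 6- and 12-month reviews fall after the cut-off on either reading.

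**2. What looks for stenosis before the cut-off.** The pre-discharge echo looks for thrombus, has no vein field and is done in one arm. The first visit concerns AF. Stenosis could still be found clinically, or on an echo done for another reason, and would then count. A zero is therefore likely but not certain.

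**3. How many cases to expect.** Inputs: 30 treated patients (*Sample Size Determination*) and an assumed true rate p. The documents give no stenosis rate. I use 0.5% and 1%, guided by the stated bound of less than 1% for any complication, and 2% as a sensitivity case above that bound. The share d of cases detected before the cut-off is also assumed: 5% or 25%, against 100% if every case were detected.

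Expected cases = 30p. P(at least one exists) = 1 − (1 − p)^30. P(zero counted) = (1 − pd)^30.

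| p | Expected cases | At least one exists | Zero counted, d = 5% | d = 25% | d = 100% |
|---|---|---|---|---|---|
| 0.5% | 0.15 | 14% | 99.3% | 96.3% | 86% |
| 1% | 0.3 | 26% | 98.5% | 92.8% | 74% |
| 2% | 0.6 | 45% | 97.0% | 86.0% | 55% |

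Zero is the most likely result in every cell, including with complete detection.

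**4. What a zero could exclude.** The exact two-sided 95% upper limit for 0 events in m patients is 1 − 0.025^(1/m). This illustrates information content only; the plan does not compute it. The values of m below 30 are assumed.

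| Patients examined, m | Upper limit for 0/m |
|---|---|
| 30 | 11.6% |
| 20 | 16.8% |
| 15 | 21.8% |
| 10 | 30.8% |
| 5 | 52.2% |

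With nobody examined there is no limit below 100%. The limits assume that those examined represent all treated patients and that all their veins were seen adequately. Chart imaging would not guarantee either.

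**The case against.** The strongest reply is that late stenosis is not lost. It is a named data item at three reviews. Adverse events are collected to 365 days and reviewed by the investigator and a surgeon outside the study, and serious ones go to the FDA and the IRB. That stands: the exclusion concerns the defined safety endpoint only, and a reader who infers that late stenosis disappears from the trial would be wrong.

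Other stronger readings also fail:

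- *The report will show 0/30 with a falsely tight limit.* The plan promises neither a separate stenosis line nor an interval. It defines one endpoint as the occurrence of any of six events. One of these is AF, in a population chosen for a baseline risk of 40% or more, so a single stenosis would hardly move the composite.
- *The one-arm echo biases a comparison between arms.* No such comparison of stenosis is described, and that echo has no vein field.
- *The adverse event form dates events by when they are first seen.* The form's date item runs onset and first observation together and can be read either way. The point has to rest on the window in *Safety endpoints*.

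It is also fair to say that 30 treated patients could not establish absence under any design, since full examination still leaves 11.6% open. This limits the importance of the point but does not remove the mismatch between endpoint and data.

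**Conclusion.** The point holds as a minor one. The 30-day window, the lack of a vein-directed examination within it, and the naming of stenosis only at later reviews all follow from the text without assumptions. So does the consequence that stenosis first found at 6 or 12 months stays outside the safety endpoint.

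The size rests on assumptions. With a true rate at or below 1%, at most 0.3 cases are expected, so few or none will be seen. How many patients would have their veins imaged, and how many cases would be found early, is not in the documents. The primary endpoint and the other five safety components are unaffected. What is at stake is whether a zero for this component is described for what it is.

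**What to change.** 1. In *Safety endpoints*, keep the 30-day window for the other five components. Count and report stenosis separately, from surgery to the 12-month assessment, using the echo and adverse event data already collected.
2. In *Data management*, add one field at each record review: whether post-operative imaging assessed the pulmonary veins, which veins, and the date.
3. Report the number of stenosis cases beside the number of treated patients with veins assessed and the latest assessment time. Keep this descriptive.
4. State in the report that stenosis was not systematically screened and that a zero does not show absence.

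An exact interval on the imaged subset should not be presented as the stenosis rate. Those patients are imaged for clinical reasons, and some reports may cover only some of the four veins.

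The cost is a text change and one added REDCap field, with no new visit, test or patient. The composite loses one component. The denominator will probably be small and selected, so it supports only a descriptive statement.
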